### 5.3.3 Toxicity assessment

Toxicity appeared during any phase of treatment will be classified according to the Common Toxicity Criteria of the National Cancer Institute (CTC AE V 4.03).

## 5.4 TREATMENT AFTER END OF STUDY

In case of treatment failure and subsequent protocol treatment schedule withdrawal, each institution shall apply the treatment they consider most appropriate.

## 5.5. STUDY PROCEDURES

Study procedures in the present protocol will include CT scans, positron emission tomography (PET) using (18F)-fluorodeoxyglucose (FDG), bone marrow biopsy and aspirate, minimal residual disease assessment, central pathology and PET review, genomic studies and patient-reported outcomes.

### 1.- Image Assessments:

- CT scans of chest, abdomen, pelvis and any other location where disease is present must be performed at screening and at scheduled timepoints (see following tables). Patients who discontinue treatment prior to disease progression must continue to have regularly scheduled CT assessments until completing the study follow-up.
- PET scan: Whole body FDG-PET must be performed at screening and a 12 months of treatment to assess response. A centralized review of the PET scan will be done following the International Response Criteria for Non-Hodgkin Lymphoma (13).

Both separate CT scan and PET scan or combined PET/CT scanner will be accepted.

### 2.- Pathology Assessments:

- **Central laboratory pathology review:** The tissue FFPE block or slides from the diagnosis will be sent to the central pathology laboratory to confirm the diagnosis and variants of MCL. The Ki-67 proliferation rate will be confirmed or determined whenever possible. The timeline of 28 days for the central review is not strict.
- **Bone marrow assessment:** Bone marrow biopsy must be obtained during screening and at 12 months when assessing the response obtained to treatment to confirm CR. IHC studies will be performed according to local laboratory pathology practice and in case of intermediate samples by morphology only. Bone marrow aspirates ~~must~~ ~~are optional~~ and ~~may~~ be considered in addition to bone marrow biopsy.

Version 3.2: September 16th, 2020

### 3.- Biomarkers and Minimal Residual Disease Assessments.

Blood samples for biomarker determination in the genomic sub-study will be collected during screening and in case of disease progression or relapse. Genomic studies including whole-exome sequencing are planned. Samples from other territories may be collected according to its availability (exceeding samples after diagnosis) and the method of preservation.

In addition, blood samples and **bone marrow aspirates will be obtained at the times described in the table of procedures in this section** for monitoring minimal residual disease by means of quantitative real-time chain reaction polymerase (qRT-PCR).

Version 3.2: September 16th, 2020

#### **4.- Patient-Reported Outcomes**

QLQ 30 and FACT-LYM questionnaires will be used for reporting the patient's outcome at screening and at 12 months of treatment.

In the following pages are summarized the procedures to be conducted in each of the stages of the study:

Multicentric phase II trial to evaluate the efficacy and safety of Ibrutinib in combination with rituximab in patients with indolent clinical forms of Mantle Cell Lymphoma

Study tests	Prior treatment initiation	First year of treatment	From second to <del>fourth</del> seventh year of treatment or follow-up	End of treatment <del>study</del> visit	Post-progression follow-up or end of study
	Day -35 y day 0	Before each cycle (monthly)	Every 3 months until end of study	30 days after end of treatment	
Informed Consent	X				
Inclusion/exclusion criteria	X				
Date of birth, date of diagnosis, clinical history	X				
Anamnesis/ Physical Examination (including ECOG and vital signs)	X	X	X	X	
Local anatomic-pathological diagnosis (1)	X				
Complete blood count (CBC). (2)	X	X	X	X	
Biochemistry (3)	X	X	X	X	
Coagulation (4)	X				
Serology (HIV, hepatitis B and C)	X				
Pregnancy Test (Urine or blood)	X				
PET/CT (5)	X	X To be performed at 12 months from treatment initiation			
CT Scan (6)		X every 6 months	X every 6 months	X	
Electrocardiogram	X				
Ejection fraction: optional. (only mandatory in patients with history of cardiopathy)	X				
Bone marrow biopsy (7)	X	X To be performed at 12			

Multicentric phase II trial to evaluate the efficacy and safety of Ibrutinib in combination with rituximab in patients with indolent clinical forms of Mantle Cell Lymphoma

		months from treatment initiation			
Bone marrow aspirate with flow cytometry (optional)	X	X To be assessed performed at 6 and 12 months from treatment initiation			
MRD assessment in peripheral blood by RQ-PCR	X* (initial study)	X every 6 months	X every 6 months	X	
Concomitant medication	X	X	X	X	
Adverse events		X	X	X	
PRO (QOL questionnaires)	X	X To be performed at 12 months from treatment initiation		X	
Overall survival follow up					X
Biological Sub-study (mandatory peripheral blood)					
Tumor sample (8)	X				X (if progression)

Version 3.2: September 16th, 2020

1: The classic, small and marginal cell MCL variants may be included after central pathology review (not strict 28 days).

2: Haemoglobin, leucocytes with differential count and platelets. Baseline determination should be done within 7 days before treatment initiation. Determinations performed before each of the cycles should be done within 72 hours before cycles.

3: Baseline (and response evaluation in 12 months, without serology): creatinine, urea, uric acid, Na, K, Ca, glucose, total protein, protein electrophoresis, albumin, IgG assessment, IgA and IgM, bilirubin, alkaline phosphatase, GGT, AST, ALT, LDH and  $\beta$ 2 seric microglobulin, serum immunofixation.

Other biochemistry: Basic biochemistry with LDH. Baseline determination should be done within 7 days before treatment initiation. Determinations performed before each of the cycles should be done within 72 hours before cycles.

4: PT, APTT, fibrinogen.

5: Period of 28 days for Baseline PET/CT is not strict: PET/CT performed within 3 months prior patient inclusion will be accepted. A broader interval may be considered for the baseline determination in specific cases.

6: Chest, abdomen and pelvis CT scan, cervical (if clinically indicated).

7: Baseline bone marrow biopsy (BMB): For this test 28 days is not strict and BMB obtained within 6 months prior to patient inclusion with stable disease will be accepted. A broader interval may be considered for the baseline determination in specific cases.

8: Peripheral blood samples will be obtained prior to initiation of treatment for obtaining purified samples of tumor and non-tumor paired cells for the biological sub-study. In other territories, exceeding diagnosis samples may be used, based on availability and means of conservation. Always when possible, a new tumor sample will be obtained, either in tissue and/or peripheral blood, in patients who have progressive or relapsing disease to carry out the second part of the sub-study that will focus on the study of Ibrutinib resistance mechanisms.

## 6. ADVERSE EVENTS NOTIFICATION

The safety monitoring of the trial will follow what is established by EU Directive 2001/20/EU and the detailed guidance on the collection, verification and presentation of adverse event/reaction reports arising from clinical trials on medicinal products for human use.

The Sponsor, through the study Chair investigator, will assess reported serious adverse events (SAE) will determine the expectedness of events reported using available safety documents and will communicate expeditiously those SAEs that are “suspected unexpected serious adverse reaction – SUSAR” to competent authorities, with the help of the monitor and site staff.

The notification to the competent authorities (drug agencies, reference EC, Local EC, and other local competent bodies, according local guidelines) and principal investigators of any reportable event is the responsibility of the Sponsor, within in the time limits established by the local regulations (suspected serious unexpected adverse reactions shall be reported to the competent authorities concerned and to the Ethics Committee concerned as soon as possible but within a maximum of 15 days of first knowledge by the sponsor, this period is reduced to 7 days in case of fatal and life-threatening SUSARs).

All adverse events during the conduction of the clinical trial (in the case of SAE from informed consent signature) and up to 30 days after the last dose of study medication, should be recorded in the CRF. In the case of serious adverse events (SAE) registration lasts until the AAG is resolved or deemed clinically stable, by medical judgment.

## 6.1 DEFINITIONS

### 6.1.1 Definition and categorization of Adverse Events

#### Adverse Event

An adverse event is any untoward medical occurrence in a clinical study subject administered a medicinal (investigational or non-investigational) product. An adverse event does not necessarily have a causal relationship with the treatment. An adverse event may therefore be any unfavourable and unintended sign (including an abnormal finding), symptom, or disease temporally associated with the use of a medicinal (investigational or non-investigational) product, whether or not related to that medicinal (investigational or non-investigational) product. (Definition per International Conference on Harmonisation [ICH]).

This includes any occurrence that is new in onset or aggravated in severity or frequency from the baseline condition, or abnormal results of diagnostic procedures, including laboratory test abnormalities.

Note: The sponsor collects adverse events starting with the signing of the ICF (refer to Section 5.3.1., All Adverse Events, for time of last adverse event recording).

#### Serious Adverse Event

A serious adverse event based on ICH and EU Guidelines on Pharmacovigilance for Medicinal Products for Human Use is any untoward medical occurrence that at any dose:

- Results in death.
- Is life-threatening (The subject was at risk of death at the time of the event. It does not refer to an event that hypothetically might have caused death if it were more severe.)
  - Requires inpatient hospitalization or prolongation of existing hospitalization.
  - Results in persistent or significant disability/incapacity.
  - Is a congenital anomaly/birth defect.
  - Is a suspected transmission of any infectious agent via a medicinal product.
  - Is Medically Important\*.

\*Medical and scientific judgment should be exercised in deciding whether expedited reporting is also appropriate in other situations, such as important medical events that may not be immediately life threatening or result in death or hospitalization but may jeopardize the subject or may require intervention to prevent one of the other outcomes listed in the definition above. These should usually be considered serious.

### 6.1.2 Adverse Event Definitions and Classifications

#### Unlisted (Unexpected) Adverse Event/Reference Safety Information

An adverse event is considered unlisted if the nature or severity is not consistent with the applicable product reference safety information. For ibrutinib, the expectedness of an adverse event will be determined by whether or not it is listed in the Investigator's Brochure.

#### Adverse Event Associated With the Use of the Drug

An adverse event is considered associated with the use of the drug if the attribution is possible, probable, or very likely by the definitions listed below.

## Attribution Definitions

### Not Related

An adverse event that is not related to the use of the drug.

### Doubtful

An adverse event for which an alternative explanation is more likely, e.g., concomitant drug(s), concomitant disease(s), or the relationship in time suggests that a causal relationship is unlikely.

### Possible

An adverse event that might be due to the use of the drug. An alternative explanation, e.g., concomitant drug(s), concomitant disease(s), is inconclusive. The relationship in time is reasonable; therefore, the causal relationship cannot be excluded.

### Probable

An adverse event that might be due to the use of the drug. The relationship in time is suggestive (e.g., confirmed by de-challenge). An alternative explanation is less likely, e.g., concomitant drug(s), concomitant disease(s).

### Very Likely

An adverse event that is listed as a possible adverse reaction and cannot be reasonably explained by an alternative explanation, e.g., concomitant drug(s), concomitant disease(s). The relationship in time is very suggestive (e.g., it is confirmed by de-challenge and re-challenge).

### Severity Criteria

An assessment of severity grade will be made using the NCI-CTCAE (version 4.03). The investigator should use clinical judgment in assessing the severity of events not directly experienced by the subject (e.g., laboratory abnormalities).

## 6.2 Special Reporting Situations

Safety events of interest on a sponsor study drug that may require expedited reporting and/or safety evaluation include, but are not limited to:

- Overdose of a sponsor study drug.
- Suspected abuse/misuse of a sponsor study drug.
- Inadvertent or accidental exposure to a sponsor study drug.
- Medication error involving a sponsor product (with or without subject/patient exposure to the sponsor study drug, e.g., name confusion).
- **Suspicion of the transmission of any infectious agent.**

Special reporting situations should be recorded in the CRF **and the Sponsor must be notified via fax ([contact]) by recording the information on the serious adverse events form.** Any special reporting situation that meets the criteria of a serious adverse event should be recorded on the serious adverse event page and the CRF.

Version 3.2: September 16th, 2020

## 6.3 Procedures

### 6.3.1 All Adverse Events

All adverse events and special reporting situations, whether serious or non-serious, will be reported from the time a signed and dated ICF is obtained until completion of the subject's last

study-related procedure (which may include contact for follow-up of safety). Serious adverse events, including those spontaneously reported to the investigator within 30 days after the last dose of study drug, must be reported.

All events that meet the definition of a serious adverse event will be reported as serious adverse events, regardless of whether they are protocol-specific assessments.

All adverse events, regardless of seriousness, severity, or presumed relationship to study drug, must be recorded using medical terminology in the source document and the CRF. Whenever possible, diagnoses should be given when signs and symptoms are due to a common etiology (e.g., cough, runny nose, sneezing, sore throat, and head congestion should be reported as "upper respiratory infection"). Investigators must record in the CRF their opinion concerning the relationship of the adverse event to study therapy. All measures required for adverse event management must be recorded in the source document.

The sponsor assumes responsibility for appropriate reporting of adverse events to the regulatory authorities. The sponsor will also report to Janssen all serious adverse events that are unlisted (unexpected) and associated with the use of the study drug. The sponsor must report these events to the appropriate Independent Ethics Committee/Institutional Review Board (IEC/IRB) that approved the protocol unless otherwise required and documented by the IEC/IRB.

### 6.3.2 Serious Adverse Events

All serious adverse events occurring during the study must be reported to **the Sponsor (see section 6.6, contact details for notification)** ~~Janssen~~ by study-site personnel within 24 hours of their knowledge of the event.

All serious adverse events that have not resolved by the end of the study, or that have not resolved upon discontinuation of the subject's participation in the study, must be followed until any of the following occurs:

- The event resolves.
- The event stabilizes.
- The event returns to baseline, if a baseline value/status is available.
- The event can be attributed to agents other than the study drug or to factors unrelated to study conduct.
- It becomes unlikely that any additional information can be obtained (subject or health care practitioner refusal to provide additional information, lost to follow-up after demonstration of due diligence with follow-up efforts).

Suspected transmission of an infectious agent by a medicinal product will be reported as a serious adverse event. Any event requiring hospitalization (or prolongation of hospitalization) that occurs during the course of a subject's participation in a study must be reported as a serious adverse event, except hospitalizations for the following:

- Hospitalizations not intended to treat an acute illness or adverse event (e.g., social reasons such as pending placement in long-term care facility).
- Surgery or procedure planned before entry into the study (must be documented in the CRF). Note: Hospitalizations that were planned before the signing of the ICF, and where the underlying condition for which the hospitalization was planned has not worsened, will not be considered serious adverse events. Any adverse event that results in a prolongation of the originally planned hospitalization is to be reported as a new serious adverse event.
- Disease progression should not be recorded as an adverse event or serious adverse event term; instead, signs and symptoms of clinical sequelae resulting from disease progression/lack of efficacy will be reported if they fulfil the serious adverse event definition.
- A standard procedure for protocol therapy administration will not be reported as a serious

adverse event. Hospitalization or prolonged hospitalization for a complication of therapy administration will be reported as a serious adverse event.

- The administration of blood or platelet transfusion. Hospitalization or prolonged hospitalization for a complication of such transfusion remains a reportable serious adverse event.
- A procedure for protocol/disease-related investigations (e.g., surgery, scans, endoscopy, sampling for laboratory tests, bone marrow sampling, pharmacokinetic or biomarker blood sampling). Hospitalization or prolonged hospitalization for a complication of such procedures remains a reportable serious adverse event.
- Prolonged hospitalization for technical, practical, or social reasons in the absence of an adverse event.
- A procedure planned before entry into the study (must be documented in the CRF). Prolonged hospitalization for a complication considered to be at least possibly related to the study drug remains a reportable serious adverse event.

### 6.3.3 Adverse Events of Interest

Specific adverse events or groups of adverse events will be followed as part of standard safety monitoring activities. These events will be reported to **the Sponsor (see section 6.6, contact details for notification) Janssen** within 24 hours of awareness irrespective of seriousness (i.e., serious and non-serious adverse events) following the procedure described above for serious adverse events and will require enhanced data collection.

#### 6.3.3.1 Major Hemorrhage

Major hemorrhage is defined as any hemorrhagic event that is Grade 3 or greater in severity or that results in 1 of the following: intra-ocular bleeding causing loss of vision, the need for a transfusion of 2 or more units of red cells or an equivalent amount of whole blood, hospitalization, or prolongation of hospitalization.

#### 6.3.3.2 Intracranial Hemorrhage

Any intracranial hemorrhage adverse event, including subdural haematoma/hemorrhage, epidural haematoma/hemorrhage and intra-cerebral hemorrhage, of any grade severity, will be captured as an event of special interest.

### 6.3.4 Other Malignancies

In addition to all routine AE reporting, all new malignant tumors, including solid tumors, skin malignancies and hematologic malignancies, are to be reported for the duration of study treatment and during any protocol-specified follow-up periods including post-progression follow-up for overall survival.

### 6.3.5 Pregnancy

All initial reports of pregnancy must be reported to **the Sponsor (see section 6.6, contact details for notification) Janssen** by the study-site personnel within 24 hours of their knowledge of the event. Abnormal pregnancy outcomes (e.g., spontaneous abortion, stillbirth, and congenital anomaly) are considered serious adverse events and must be reported as a Serious Adverse Event. Any subject who becomes pregnant during the study must discontinue further study treatment.

Because the effect of the study drug on sperm is unknown, pregnancies in partners of male subjects included in the study will be reported by the study-site personnel within 24 hours of their

knowledge of the event.

Follow-up information regarding the outcome of the pregnancy and any postnatal sequelae in the infant will be required.

## 6.4 PRODUCT QUALITY COMPLAINT HANDLING

A product quality complaint (PQC) is defined as any suspicion of a product defect related to manufacturing, labelling, or packaging, i.e., any dissatisfaction relative to the identity, quality, durability, or reliability of a product, including its labelling or package integrity. A PQC may have an impact on the safety and efficacy of the product. Timely, accurate, and complete reporting and analysis of PQC information from studies are crucial for the protection of subjects, investigators, and the sponsor, and are mandated by regulatory agencies worldwide.

### 6.4.1 Procedures

All initial PQCs must be reported to **the Sponsor (see section 6.6, contact details for notification) Janssen** by the study-site personnel within 24 hours after being made aware of the event.

If the defect is combined with a serious adverse event, the investigational staff must report the PQC to **the Sponsor (see section 6.6, contact details for notification) Janssen** according to the serious adverse event reporting timelines. A sample of the suspected product should be maintained for further investigation if requested by **the Sponsor. Janssen**.

## 6.5. PREGNANCY NOTIFICATION

The pregnancy of a female patient or partner of a male patient, not being itself a serious adverse event, it should be also expeditiously managed like a SAE. It should be registered and notified with a specific form for pregnancy events and reported on an expedited basis (within 24 hours since first knowledge), even a voluntary or spontaneous discontinuation occurs, describing the details of the birth and presence or absence of a defect in the foetus or a congenital abnormality.

Potential effects on spermatogenesis: pregnancies that occur in the partner of a male patient should also be notified within 24 hours by the specific form of pregnancy and followed until the end, although a voluntary or spontaneous discontinuation occurs, describing details of the birth and the presence or absence of a defect in the foetus or a congenital abnormality. It will also indicate to the patient pregnant couple that should immediately contact her doctor.

To carry out the monitoring of clinical data in pregnancy, it should be requested pregnant authorization either in case of study patient or partner of a male patient, which will be documented with the signing of the "Express consent to disclosure medical data on pregnancy". This form should not be sent to the monitor / CRO, but will be kept on file with the other study documentation at the Site.

## **6.6. CONTACT DATA FOR SAE, PREGNANCY, DEATH AND QUALITY CLAIMS NOTIFICATIONS, SPECIAL SITUATION REPORTS**

**DEPARTAMENTO DE INVESTIGACIÓN MFAR, S.L.**

**[contact]**

**e-mail: [[contact]](mailto:[contact])**

**Version 3.2: September 16th, 2020**

## **7. STATISTICAL CONSIDERATIONS**

Our study proposal is looking for a therapeutic alternative to conventional immunochemotherapy (R-CHOP) in clinically indolent MCL.

This phase II study will explore the feasibility of Ibrutinib plus Rituximab combination in this subset of patients evaluating its capacity of inducing a high response rate with a favourable toxicity profile. In addition, an extensive biological study of the cases will be conducted in order to explore clinic-biological correlations.

We hypothesize that for a CR rate of 30% usually achieved with R-CHOP, the combination of Ibrutinib plus Rituximab will be able to exceed this proportion in 20%.

We propose a Phase II study with a two-stage design with error probabilities  $\alpha$  and  $\beta$  of 0.10 and 0.2 respectively. The optimal design will have an expected sample size of 50 patients (at least 46 patients evaluable for response).

The first stage will consist of 15 patients. If 5 or less complete responses are observed the trial is terminated, otherwise accrual can continue to a total of 50 patients.

For Primary Analysis we plan the evaluation of CR rate at 6 months from the start of therapy. All the patients will be evaluated with Thoracoabdominopelvic CT and bone marrow aspirate at that point. If 5 or less complete responses are observed among the first 15 patients recruited and evaluated, the trial will be terminated.

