Secondary Endpoints	
 
1. To determine the overall response rate (ORR) at 12 months, Progression free survival (PFS), duration of response (DOR) and overall survival (OS).
 
2. To determine the rate of negative minimal residual disease (MRD), the time to obtain a molecular response and the median duration of the molecular response in I+R responding patients.
 
3. Rates of AEs, SAEs, and SUSARs by CTC grade (Version 4.03) during I+R treatment
 
4. To assess the health-related quality of life (QOL) during treatment.
 
5. Genomic studies in indolent clinical forms of MCL (IGHV mutational status, DNA copy-number and whole exome sequencing).
 

Sample Size	
First Stage: 15 patients
 
Second Stage: If at least 6 patients show a complete response during first stage, the study will continue until inclusion of 50 patients.

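### The stated alpha of 0.10 does not generate the stated optimal design (15 patients, then 46 evaluable), which is the optimal design at one-sided 0.05; and 50 is the maximum enrolment, not the expected sample size

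*Protocol*

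**What the plan says.** Protocol Section 7 sets the hypothesis: "We hypothesize that for a CR rate of 30% usually achieved with R-CHOP", the combination "will be able to exceed this proportion in 20"%. It proposes a two-stage design and gives alpha, then beta, as follows: "of 0.10 and 0.2 respectively. The optimal design will have an expected sample size of 50 patients (at least 46 patients evaluable for response"). The sidedness of alpha is not given.

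Stage 1 has 15 patients. The rule is: "If 5 or less complete responses are observed the trial is terminated, otherwise accrual can continue to a total of 50 patients". The Sample Size entry of the Section 1 synopsis agrees: with at least 6 complete responses in stage 1, "the study will continue until inclusion of 50 patients". The only boundary in the protocol is the one for stage 1.

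**The concern.** An optimal two-stage design follows from four inputs: the null rate, the target rate, alpha and beta. Section 7 gives all four, so its sample sizes can be checked. The stage 1 rule agrees with them, but the total of 46 evaluable patients does not. The term expected sample size also has a fixed meaning in such a design: the average over trials that stop early and trials that do not. It cannot equal the maximum unless early stopping is impossible.

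At stake is the success boundary for the primary objective. A statistician who starts from alpha 0.10 and one who starts from 15 and 46 arrive at different numbers of complete responses for a positive trial.

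**Working it through.** **Inputs (all from protocol Section 7).** Null CR rate p0 = 0.30. Target p1 = 0.30 + 0.20 = 0.50, reading the 20% as percentage points. Alpha 0.10, beta 0.20. Stage 1: n1 = 15, stop at r1 = 5 or fewer. Evaluable total n = 46, enrolment 50 (an allowance of 4/50 = 8%).

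**Formulas.** With success at c or more CR in total, X ~ Bin(15, p) and Y ~ Bin(n − 15, p):

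- P(success | p) = Σ over x = 6,…,15 of P(X = x) · P(Y ≥ c − x). This is alpha at p0 and power at p1.
- P(early stop | p) = P(X ≤ 5).
- Expected N = 15 + [1 − P(early stop)] · (n − 15).

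The optimal design has the smallest expected N under p0 among those meeting both error limits; the minimax design has the smallest maximum N. Both were found by exhaustive search with exact binomial probabilities. Below, r/n means that r or fewer responses among n is a failure.

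**Step 1: which inputs reproduce the plan's figures?**

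| alpha, beta | Optimal design | Exact alpha | Power | Expected N at 30% |
|---|---|---|---|---|
| 0.10, 0.20 (as stated) | 5/15, 12/32 | 0.0997 | 0.804 | 19.7 |
| 0.05, 0.20 | 5/15, 18/46 | 0.0499 | 0.803 | 23.6 |
| 0.10, 0.10 | 7/22, 17/46 | 0.0974 | 0.905 | 29.9 |
| 0.05, 0.10 | 8/24, 24/63 | 0.0497 | 0.903 | 34.7 |

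Only one-sided alpha 0.05 with beta 0.20 gives 5, 15 and 46 together. At the stated pair the optimal total is 32, and the minimax design (3/12, 11/28) has 28. The stage 1 rule 5/15 is the same in the first two rows, so the interim rule does not depend on which alpha was meant.

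**Step 2: expected sample size.** P(early stop) is 0.7216 at 30% and 0.1509 at 50%.

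- Maximum 46: 15 + 0.2784 × 31 = 23.6, and 15 + 0.8491 × 31 = 41.3.
- Maximum 50: 15 + 0.2784 × 35 = 24.7, and 15 + 0.8491 × 35 = 44.7.

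None of these is 50.

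**Step 3: what each boundary delivers after stage 1 is passed (6 or more of 15).**

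| Evaluable | Success at | Alpha | Power |
|---|---|---|---|
| 46 | ≥17 | 0.116 | 0.840 |
| 46 | ≥18 | 0.0795 | 0.827 |
| 46 | ≥19 | 0.0499 | 0.803 |
| 50 | ≥18 | 0.125 | 0.844 |
| 50 | ≥19 | 0.089 | 0.836 |
| 50 | ≥20 | 0.0585 | 0.821 |
| 50 | ≥21 | 0.0355 | 0.795 |

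With 46 evaluable, the lowest boundary within alpha is 18 at one-sided 0.10 and 19 at one-sided 0.05. With 50 evaluable, it is 19 and 21. The contested results are therefore 18 of 46, and 19 or 20 of 50. Carrying the 46-patient boundary (≥19) over to 50 evaluable patients raises alpha from 0.050 to 0.089.

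**The case against.** The strongest reply is that 0.10 may be a two-sided level. It then corresponds to one-sided 0.05, and 5/15 with 46 reproduces exactly. This stands as a possible explanation, but the protocol does not say it. As the design rejects only upward, its false-positive probability would be 0.05, not 0.10, so the label still needs correcting.

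A second reply is that *expected* is loose wording for *planned*. That is plausible, since the synopsis and the rest of Section 7 treat 50 as the total. Nobody would run the trial differently because of that word. It is still the wrong term beside *optimal design*, where it has a technical meaning.

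A reader might also infer more than the documents support:

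- **That the error rates are inflated or the trial is underpowered.** With ≥18 or ≥19 of 46, or ≥19 or ≥20 of 50, alpha stays at or below 0.10 and power at or above 0.80. The sample is larger than alpha 0.10 requires.
- **That beta is wrong too.** It is not: 5/15, 18/46 has power 0.803.
- **That the final boundary is undefined.** It may stand in a statistical analysis plan that is not at hand, so its absence from the protocol is not itself an error. It can also be derived as 18/46 from the stated 5, 15, 46 and *optimal*. The problem is that starting from alpha 0.10 gives another answer.
- **That 18, 19 and 20 responses are all ambiguous.** That depends on the denominator. With 46 evaluable, 19 and 20 succeed at either level.

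**Conclusion.** The point holds in a limited form. The alpha in Section 7 is not that of the optimal design with 15 and 46 patients; that design has one-sided alpha 0.05. Fifty is the maximum enrolment, against an expected size of 23.6 to 41.3 (maximum 46) or 24.7 to 44.7 (maximum 50). Beta and the interim rule are consistent with the design. The consequence is two competing success boundaries: 18 against 19 of 46, and 19 against 21 of 50.

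Three assumptions apply. The 20% is an absolute difference, which is supported by the exact match at 30% against 50%. Alpha is one-sided unless stated otherwise. The same CR definition and time point apply at both stages. The last does not yet hold in the text: Section 7 assesses CR at 6 months by CT and marrow aspirate, while Sections 5.1 and 5.3.2 define the primary endpoint at 12 months by PET-CT and marrow biopsy. Until these are reconciled, the rates above describe the design as specified, not necessarily the error rates this trial attains.

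**What to change.** Restate Section 7 with p0 = 30%, p1 = 50% (20 percentage points), the sidedness of alpha, and 50 as the maximum enrolment with at least 46 evaluable. Then choose one of two courses:

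1. **One-sided alpha 0.05, power 0.80.** Keep *optimal* and give the design as 5/15, 18/46, with success at ≥19 of 46 (0.0499, 0.803) and expected N 23.6 under 30%. If all 50 are evaluable, success is at ≥21 (0.036, 0.795).
2. **One-sided alpha 0.10, if that is intended.** Drop *optimal* and give the boundary with its attained rates: ≥18 of 46 (0.080, 0.827) or ≥19 of 50 (0.089, 0.836).

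Either way, state or cross-refer to the boundary for evaluable totals between 46 and 50. First reconcile the time point and assessment method of CR in Section 7 with Sections 5.1 and 5.3.2, because the quoted rates assume a single CR definition. The sponsor must say which alpha was meant; the documents do not settle it.

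The cost is wording only: no added patients and no change to the interim rule. The one statistical price is under course 1 with all 50 evaluable, where power is 79.5%, just under 80%.
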